9.2 Setting

The study will take place in single country (Korea) with multiple centers. The study sites will be identified and selected by AbbVie. The study population shall comprise of male

and/or female patients who are attending a routine clinical visit and meet all of the inclusion criteria and none of the exclusion criteria. Overall, approximately 89 subjects with clinically diagnosed RA are planned to be enrolled in the study at up to 9 sites.

The recruiting investigators will select potentially eligible patients from consecutive visits within their clinic based on the inclusion and exclusion criteria (Section 9.2.1 and Section 9.2.2). It is the responsibility of each physician to ask every consecutive patient who meets the inclusion criteria of the study to participate to avoid selection bias, and if investigators hold different types of clinics (e.g. routine visit clinics versus emergency clinics), only patients visiting their routine clinics will be used for patient selection. Site personnel should thoroughly assess the eligibility criteria and evidence of this should be stored with the source documentation at site.

Where there is any deviation from the inclusion/exclusion criteria, the patient should be excluded from the study.

9.2.1 Inclusion Criteria:

Patients meeting all of the following inclusion criteria at baseline will be included:

1. Subject has a diagnosis of RA as defined by the 1987 revised ACR classification criteria and/or the ACR/ the European League against Rheumatism (EULAR) 2010 classification criteria (any duration since diagnosis)
2. Male or female subjects ≥ 18 years of age (local definition according to adalimumab label) who is in compliance with eligibility for adalimumab based on the local label
3. Patients with moderate to severe RA defined as DAS28 (ESR) or DAS28 (CRP) >3.2
4. Biologically treatment naïve and initiated adalimumab at baseline visit
5. Availability of clinical data of the previous 12 weeks prior to baseline
6. Ability to self-complete patient questionnaires
7. Subject must be able and willing to provide written informed consent and comply with the requirements of this study protocol

9.2.2 Exclusion Criteria:

Patients meeting any of the following exclusion criteria at baseline will be excluded:

1. Patients who are pregnant or breast feeding at enrolment or wish to become pregnant in the next 24 weeks

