9.2.4.7 Study Documents

Clinical case report form (CRF)

The clinical CRF will document the patient's current status (moderate, severe RA), Disease Activity Score in 28 joints (DAS28), prior and current treatments and other relevant clinical and demographic data to be used in segmenting the population during analysis.

To calculate the DAS28 the physician or specialist nurse will:

1. Count the number of swollen joints (out of the 28)
2. Count the number of tender joints (out of the 28)
3. Take blood to measure the erythrocyte sedimentation rate (ESR) or C reactive protein (CRP); the latest measurement in the medical records may also be used if a blood draw is not standard for that visit
4. Ask the patient to make a 'global assessment of health' which will be indicated by marking a 10 cm line between very good and very bad

The physician or specialist nurse will then mark each component score on the CRF and the DAS28 score if calculated (an online scoring calculator for the DAS28 can be found at <http://www.das-score.nl/das28/DAScalculators/dascalculators.html>).

The DAS28 will be scored using the following formula:

$$\text{DAS28 ESR} = 0.56 * \text{sqrt}(\text{tender28}) + 0.28 * \text{sqrt}(\text{swollen28}) + 0.70 * \ln(\text{ESR}) + 0.014 * (\text{Global assessment of Health in cm})$$

$$\text{DAS28 CRP} = 0.56 * \text{sqrt}(\text{tender28}) + 0.28 * \text{sqrt}(\text{swollen28}) + 0.36 * \ln(\text{CRP}) + 0.014 * (\text{Global assessment of Health in cm}) + 0.96$$

DAS28 scores will be interpreted using the following categorization:

- Remission: DAS28 \leq 2.6
- Low Disease activity: $2.6 < \text{DAS28} \leq 3.2$
- Moderate Disease Activity: $3.2 < \text{DAS28} \leq 5.1$
- High Disease Activity: DAS28 > 5.1

The full CRF is presented in Appendix C.

PRO questionnaires

The following PRO questionnaires will be included in the patient questionnaire packet.

Health Assessment Questionnaire Disability Index (HAQ DI)

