#### **3.5.2      *Exposure/Independent Variables of Interest***

- **Patient demographics (if data available)**

- Date of birth
- Age at baseline
- Age groups
- Gender at birth
- Marital status (married, unmarried)
- Medical plan type
  - ✓ The type of healthcare plan each patient is enrolled in at baseline will be determined, including National/Public insurance, Private insurance, Employer benefits, and Other

- **Clinical characteristics**

- Initial Diagnosis of Rheumatoid Arthritis (RA)
  - ✓ Year of initial diagnose
- Initiation of Adalimumab
  - ✓ First time administration (DD/MM/YYYY)
  - ✓ Dosage of first injection (in mg)
- Disease status of RA
  - ✓ Moderate (defined as Disease Activity Score in 28 Joints (DAS28) between 3.2 and 5.1)
  - ✓ Severe (DAS28>5.1)
- Erythrocyte sedimentation rate (ESR) (in mm/hour)
- C reactive protein (CRP) (in mg/L)
- Disease Activity Score in 28 joints (DAS28)

To calculate the DAS28, the physician or specialist nurse will:

1. Count the number of swollen joints (out of the 28)
2. Count the number of tender joints (out of the 28)
3. Take blood to measure the erythrocyte sedimentation rate (ESR) or C reactive protein (CRP); the latest measurement in the medical records may also be used if a blood draw is not standard for that visit
4. Ask the patient to make a ‘global assessment of health’ which will be indicated by marking a 10 cm line between very good and very bad

The physician or specialist nurse will then mark each component score on the CRF and the DAS28 score if calculated (an online scoring calculator for the DAS28 can be found at <http://www.das-score.nl/das28/DAScalculators/dascalculators.html>).

The DAS28 will be scored using the following formula:

$$\text{DAS28} = 0.56 * \text{sqrt}(\text{tender28}) + 0.28 * \text{sqrt}(\text{swollen28}) + 0.70 * \ln(\text{ESR or CRP}) + 0.014 * (\text{Global assessment of Health})$$

DAS28 scores will be interpreted using the following categorization:

- ✓ Remission: DAS28  $\leq$  2.6
- ✓ Low Disease Activity:  $2.6 < \text{DAS28} \leq 3.2$
- ✓ Moderate Disease Activity:  $3.2 < \text{DAS28} \leq 5.1$
- ✓ High Disease Activity: DAS28  $> 5.1$
- comorbidities
  - ✓ Myocardial infarction
  - ✓ Congestive heart failure
  - ✓ Peripheral vascular disease
  - ✓ Cerebrovascular disease
  - ✓ Dementia
  - ✓ Chronic pulmonary disease
  - ✓ Connective tissue disease
  - ✓ Ulcer disease
  - ✓ Mild liver disease
  - ✓ Diabetes
  - ✓ Hemiplegia

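### The protocol's DAS28 formulas weight a 0–10 cm global assessment by 0.014, so the patient's rating adds at most 0.14 points, and the SAP repeats the weight without a unit

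*Protocol*

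**What the plan says.** Protocol 9.2.4.7 (clinical CRF) has the patient give a global assessment, "which will be indicated by marking a 10 cm line between very good and very bad". It then states: "The DAS28 will be scored using the following formula". Two formulas follow, one for ESR and one for CRP. In both, the last patient-derived term is 0.014 multiplied by "Global assessment of Health in cm". The results are classified with cut-offs of 2.6, 3.2 and 5.1. The same paragraph links an online DAS28 calculator.

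SAP 3.5.2 repeats the step in which the patient makes a "global assessment of health" on a 10 cm line. It prints the same 0.014 weight and the same cut-offs, but gives no unit in the formula.

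The baseline, follow-up and early termination CRFs (Appendices C and K) ask for the latest DAS28 score if one was calculated, and a footnote sends the site to the protocol for the calculation.

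DAS28 is an entry criterion (protocol 9.2.1): "Patients with moderate to severe RA defined as DAS28 (ESR) or DAS28 (CRP) >3.2". SAP 3.5.2 also uses it to separate moderate from severe disease, and SAP 5.5 makes it the severity measure in Tables 9.1 and 9.2.

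**The concern.** A composite score needs each weight to match the unit of its component. Here the weight is applied to a variable that runs only from 0 to 10, which makes one of the four components nearly inert. The SAP does not help the programmer: the same marked line can be entered as 0–10 or as 0–100, a tenfold difference in the term, while the cut-offs stay fixed.

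Two things are at stake. The first is the level of DAS28, and so recorded eligibility and the moderate or severe label. The second is comparability. If some scores come from the printed formula and others from a calculator on a different scale, DAS28 would differ between sites, or between visits of one patient, for reasons unrelated to disease. The label, or the score itself, is used in the severity subgroups (protocol 9.7.3), the ANOVA adjusted for baseline severity (protocol 9.7.4 and 9.7.5; SAP 5.3), the modifier analyses (protocol 9.7.8; SAP 5.6) and the association models (SAP 5.5).

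**Working it through.** The plan states no numerical result for this term, so there is no figure to reproduce. The check evaluates the printed formulas.

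**Inputs**
- Protocol 9.2.4.7: line length 10 cm; weight 0.014, unit cm; joint terms 0.56 × √tender and 0.28 × √swollen, with counts out of 28; inflammation term 0.70 × ln(ESR), or 0.36 × ln(CRP) + 0.96.
- Cut-offs 2.6, 3.2 and 5.1 (protocol 9.2.4.7 and SAP 3.5.2).
- G is the global assessment in cm.

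**Step 1: weight of the global term as printed (no outside assumption)**
- Maximum global contribution: 0.014 × 10 = 0.14.
- Maximum tender contribution: 0.56 × √28 = 2.96.
- Maximum swollen contribution: 0.28 × √28 = 1.48.

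**Step 2: gap between the two readings**

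Assumption: 0.014 and the cut-offs belong to a 0–100 reading, so the term is 0.014 × 10G. Its maximum is then 0.014 × 100 = 1.40. The gap is 0.014 × (10G − G) = 0.126 × G.

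| G (cm) | 0 | 2 | 5 | 8 | 10 |
|---|---|---|---|---|---|
| Gap (points) | 0 | 0.25 | 0.63 | 1.01 | 1.26 |

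For scale, the moderate band is 5.1 − 3.2 = 1.9 points wide.

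**Step 3: can the gap move a patient across a cut-off?**

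These are illustrative patients, not study data.

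| Version | Tender | Swollen | ESR or CRP | G (cm) | Sum without G | As printed | 0–100 reading | Crosses |
|---|---|---|---|---|---|---|---|---|
| ESR | 0 | 1 | 20 | 4 | 2.377 | 2.433 | 2.937 | 2.6 |
| ESR | 2 | 2 | 15 | 5 | 3.084 | 3.154 | 3.784 | 3.2 |
| ESR | 6 | 6 | 30 | 6 | 4.438 | 4.522 | 5.278 | 5.1 |
| CRP | 2 | 2 | 5 | 5 | 2.727 | 2.797 | 3.427 | 3.2 |
| CRP | 8 | 6 | 15 | 7 | 4.205 | 4.303 | 5.185 | 5.1 |

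Second row in full: 0.56√2 + 0.28√2 + 0.70 ln 15 = 0.792 + 0.396 + 1.896 = 3.084. Adding 0.014 × 5 = 0.07 gives 3.154; adding 0.014 × 50 = 0.70 gives 3.784.

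**Step 4: effect on change scores**
- If the rating improves from 7 to 2 cm, the term changes by 0.014 × 5 = 0.07 as printed and by 0.014 × 50 = 0.70 on the 0–100 reading.
- If the rating stays at 5 cm but the scale differs between visits, DAS28 appears to change by 0.63 with no change in the patient.

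**Step 5: where DAS28 does not enter**

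The primary test is a paired t-test on HAQ DI change without severity adjustment (protocol 9.7.4; SAP 5.3). The sample size (protocol 9.5) uses only HAQ DI and work time lost.

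**The case against.** The documents do not say which scale the 0.014 weight and the cut-offs were built for. From the text alone one can show that the term is at most 0.14, not that 0.14 is wrong. This objection stands: the downward shift and any preferred unit are conditional.

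A reader might also infer that the protocol and SAP contradict each other on the unit. They do not. The SAP omits the unit while repeating the 10 cm line, and neither document prints mm in the formula. What remains is an ambiguity.

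The printed term is not negligible against every joint change. The first tender joint adds 0.56, but because counts enter as square roots, going from 8 to 9 tender joints adds only 0.56 × (3 − 2.828) = 0.096, less than 0.14. The fair comparison is between maxima, and there the term is still small.

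Nor do the documents show that sites used the printed formula. A calculator is linked, its scale is not described, and the CRF takes a score only if one was calculated. Entry is allowed on either the ESR or the CRP version, and no baseline distribution is given, so misclassification is possible but not demonstrated. The planned end of data collection was 28 February 2018, and the approvals of Amendment 01 are dated March and April 2018, so a correction cannot alter who was enrolled.

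These points limit the reach of the finding. They do not remove it, because the protocol presents the cm formula as the scoring rule and the CRFs direct sites to it.

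**Conclusion.** The point holds as a scoring problem that should be fixed. As printed, one of four DAS28 components contributes at most 0.14 points, and the SAP leaves the scale of that component open. Both statements follow from the documents alone.

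On the assumption that the weight and cut-offs are meant for a 0–100 reading, the printed formula scores a patient lower by 0 to 1.26 points (0.63 at 5 cm) and can change the category at 2.6, 3.2 or 5.1. If sites used two routes with different scales, DAS28 would also carry spurious differences between sites or visits.

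The exposure covers recorded eligibility, moderate or severe grouping, the severity-adjusted sensitivity ANOVA, the modifier analyses and Tables 9.1 and 9.2. For the ANOVA and the modifier analyses this takes severity as SAP 3.5.2 defines it, from DAS28.

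A reader might conclude that every DAS28 in the study is too low, or that patients were wrongly included or excluded. The documents do not support that: there is no shift at a rating of 0, the route used by sites is unknown, and the reference scale is not stated. Nor is the primary result at issue, since neither the HAQ DI paired t-test nor the sample size uses DAS28.

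**What to change.** - Check the 0.014 weight against the scale of the DAS28 instrument. Then print one matching unit and weight in protocol 9.2.4.7 (both formulas) and in SAP 3.5.2. If the assumption above is confirmed, that means 0.014 with a 0–100 reading or, equivalently, 0.14 with a 0–10 reading.
- Name one DAS28 source for analysis: the site-entered score or a centrally computed one.
- In the SAP, recompute DAS28 centrally with the agreed formula wherever the global assessment was recorded, and flag site-entered scores that differ by more than rounding.
- Before that, confirm where the rating is held. The protocol says each component is marked on the CRF, but the CRF text in Appendices C and K shows fields for joint counts, ESR or CRP and the DAS28 score, and none for the global assessment (figures are missing from the text available). It may be only in source records.
- Where DAS28 cannot be recomputed, report the DAS28 analyses with that limitation.

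The cost is an edit to three formula lines, a sentence naming the source, and a programming check. No new visits are needed. If the rating is not on the CRF, retrieving it from source records is extra work for the sites.

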Appendix C. Clinical Case Report Form (CRF)

Baseline:

1023259 Real-World Impact of RA
____ - ____
Site number Participant ID

Clinician Case Report Form (Baseline)

All of the following information must be completed by the clinician or his/her representative.

Clinician name: _____

Clinician signature: _____

[figure not shown]
Patient ID	

____	____	

Site #	Participant #	

	____	____	Site #	Participant #														
____	____																		
Site #	Participant #																		
Today's date	

____	____	/	____	____	/	____	____	____	

Day	Month		Year						

	____	____	/	____	____	/	____	____	____	Day	Month		Year					
____	____	/	____	____	/	____	____	____											
Day	Month		Year																

Please provide the information below.

1. When was the patient diagnosed with Rheumatoid Arthritis?	

____	____	____	____	

Year	

	____	____	____	____	Year			
____	____	____	____						
Year									
2. What is the patient's current disease status?	 Moderate  Severe								

1023259 Real-World Impact of RA
 -
 Site number Participant ID

imshealth™
 INTELLIGENCE APPLIED.

Please provide the information below.		
3. Please perform a swollen and tender joint examination on your patient using the figure below and record the total number of tender/swollen joints in the appropriate boxes on the right.	  Tender Joint Count	  Swollen Joint Count
If diagnosis is RA:		
4. Please record the most recent Erythrocyte Sedimentation Rate (ESR) (in mm/hour) or C-reactive protein (CRP) (in mg/L) of this patient.	  ESR (mm/hour) Test Date (DD/MM/YYYY): ____/____/_____	
	  CRP (mg/L) Test Date (DD/MM/YYYY): ____/____/_____	
5. Please record the latest DAS28 score*, if calculated		

* For calculation instruction, please refer to study protocol, page 21, clinical case report form (CRF).

1023259	Real-World Impact of RA
Site number	Participant ID

6. Please check all the comorbidities this patient has currently.

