#### **5.5 Analysis Plan for Additional Secondary Objectives**

- Descriptive statistics will be presented for post-index overall RA related direct healthcare resource utilization (Excel Table 8)

- Consultations/visits to healthcare professionals for treatment of RA (number of patients with  $\geq 1$  visit; categorized by the treatment department listed in 3.5.4)
- Procedures received when visiting the healthcare professional(s) for treatment of RA (number of patients with  $\geq 1$  procedure; categories listed in 3.5.4)
- surgeries received when visiting the healthcare professional(s) for treatment of RA (number of patients with  $\geq 1$  surgery; categories listed in 3.5.4)
- Hospitalizations in relation to RA (number of patients with  $\geq 1$  admission)
- Length of stay in days (mean, SD, median)
- Concomitant medications taken for RA (number of patients with  $\geq 1$  medication; categories listed in 3.5.4))

- Associations between disease severity (measured by DAS28) and PROs (HAQ DI score, SF-36 domain scales, EQ-5D-3L index, WPAI outcomes) will be analyzed using the bivariate linear regression model (Excel Table 9.1). Separate models will be estimated to identify the association between DAS28 and each of the PROs.
- Additionally, in Excel Table 9.2, separate bivariate liner regression models will be estimated to identify the association between change in DAS28 and change in each of the PROs at 12 and 24 weeks after baseline respectively.

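### The CRP term in both DAS28 formulas has no offset inside the logarithm, so the score does not exist at CRP 0 and falls without limit below 1 mg/L

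*Protocol*

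**What the plan says.** Protocol 9.2.4.7 introduces two formulas, one for ESR and one for CRP, with "The DAS28 will be scored using the following formula". The CRP version ends in "0.36 * \ln(\text{CRP}) + 0.014 * (\text{Global assessment of Health in cm}) + 0.96". SAP 3.5.2 prints a single formula for either marker, with "0.70 * \ln(\text{ESR or CRP" as the marker term and no added constant.

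The CRF in Protocol Appendix C asks for the most recent ESR or "C-reactive protein (CRP) (in mg/L) of this patient". It gives no lower reporting limit and no instruction for a result of zero or below detection. The protocol also points sites to an online calculator and lets them enter a score they have already calculated.

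The category cut-offs include "Remission: DAS28 \leq 2.6" and "Low Disease activity: $2.6 < \text{DAS28} \leq 3.2". SAP 3.5.5 and Protocol 9.7.9 allow no imputation beyond questionnaire items (and, in the SAP, incomplete dates). SAP 5.5 regresses each PRO on DAS28 (Table 9.1) and fits models to "identify the association between change in DAS28 and change in each of the PROs at 12 and 24 weeks" (Table 9.2).

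**The concern.** The logarithm of zero has no value, and the logarithm of a number below 1 is negative and unbounded. CRP in mg/L can plausibly reach that range once inflammation is controlled. The formula would then lose, or push to an extreme, the scores of patients who have responded well.

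At stake are the DAS28-PRO associations in Tables 9.1 and 9.2, where a few very low scores could act as high-leverage points and zero-CRP visits would drop out. DAS28-based severity is also exposed. The SAP defines moderate and severe disease by DAS28, and baseline severity enters the sensitivity ANOVA for HAQ DI (SAP 5.3) and the effect-modifier models (SAP 5.6). The eligibility threshold of 3.2 uses the same score.

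The defect is distinct from the conflict between the protocol and SAP formulas: adopting the protocol's version in the SAP would leave it in place.

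**Working it through.** The plan states no figure to reproduce here, so the check evaluates the printed formulas.

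**Inputs.** Protocol CRP term 0.36 × ln(CRP), constant 0.96 and cut-offs 2.6 and 3.2 (Protocol 9.2.4.7); SAP term 0.70 × ln(CRP) (SAP 3.5.2); CRP in mg/L (Appendix C). The comparator is an assumption: an offset c of +1 mg/L, with +0.5 mg/L to show the range. Neither document contains an offset. The CRP values are illustrative, because the documents give no CRP distribution or assay limit.

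**Step 1: the term itself.** At CRP 0 it is undefined in both documents. At low positive values:

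| CRP (mg/L) | 0.36 ln(CRP) | 0.36 ln(CRP+0.5) | 0.36 ln(CRP+1) | SAP 0.70 ln(CRP) |
|---|---|---|---|---|
| 20 | 1.078 | 1.087 | 1.096 | 2.097 |
| 5 | 0.579 | 0.614 | 0.645 | 1.127 |
| 1 | 0 | 0.146 | 0.250 | 0 |
| 0.5 | -0.250 | 0 | 0.146 | -0.485 |
| 0.1 | -0.829 | -0.184 | 0.034 | -1.612 |

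A fall from 1 to 0.1 mg/L alone moves the protocol score by 0.36 × ln(10) = 0.83, more than the low-activity band (3.2 - 2.6 = 0.6). Under the SAP weight it moves by 0.70 × ln(10) = 1.61. With every other component at zero, the protocol score is negative below CRP = exp(-0.96/0.36) = 0.069 mg/L.

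**Step 2: effect on change.** For baseline b and follow-up f, omitting an offset c adds 0.36 × [ln(1 + c/f) - ln(1 + c/b)] to the measured improvement. This is positive whenever CRP falls to a positive value, for any c above zero. With b = 20, f = 0.5 and c = 1 it is 0.36 × [ln(3) - ln(1.05)] = 0.378.

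| CRP 20 to | Change without offset | Excess, c = 0.5 | Excess, c = 1 |
|---|---|---|---|
| 5 | 0.499 | 0.025 | 0.048 |
| 3 | 0.683 | 0.047 | 0.086 |
| 1 | 1.078 | 0.137 | 0.232 |
| 0.5 | 1.328 | 0.241 | 0.378 |
| 0.1 | 1.907 | 0.636 | 0.846 |

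The baseline value matters little: with baselines of 10 to 40 mg/L, the c = 1 excess at 0.5 mg/L is 0.36 to 0.39.

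**Step 3: one worked patient.** Take tender joints 8 to 4, swollen joints 6 to 3, global assessment 6 to 3 (in cm, as the protocol prints it) and CRP 20 to 0.5 mg/L. Follow-up as printed is 1.120 + 0.485 - 0.250 + 0.042 + 0.96 = 2.36, which is remission. With +1 the CRP term is 0.146 and the score is 2.75, which is low activity. The improvement is 2.03 as printed and 1.66 with the offset. The crossing of a cut-off depends on the components chosen; the difference in change does not.

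**Step 4: interaction with the SAP formula.** For CRP 20 to 0.5, the CRP contribution is 0.70 × ln(40) = 2.58 in the SAP and 0.36 × ln(40) = 1.33 in the protocol. That gap of 1.25 is over three times the 0.38 at issue here.

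**The case against.** Several stronger readings are tempting, and the documents do not support them.

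- *Improvement is overstated in every patient whose CRP normalises.* The documents give no normal range. If CRP falls from 20 only to 3-5 mg/L, the excess is below 0.1. It becomes material at about 1 mg/L and below, and how many patients reach that level is unknown.
- *The error biases the study result in favour of adalimumab.* Protocol 9.3 lists change in disease severity as an additional secondary variable, but its only planned analysis is its association with PRO change. SAP section 6 lists no table that tests DAS28 change. DAS28 categories are tabulated at baseline only (SAP 5.2), where the forms nearly agree if CRP is high.
- *Patients with CRP 0 are dropped.* SAP 3.5.5 analyses available data, so only that visit's CRP-based score is lost. The CRF also has an ESR field, so an ESR score may exist. A missing score does not itself overstate improvement.

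Three further objections stand. The size depends on an offset that is in neither document. A site-entered score may come from the online calculator, whose formula cannot be seen here. Adding an offset to the SAP's 0.70 term alone would leave it in conflict with the protocol, so the formulas have to be reconciled first.

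None of this removes the core defect: both prescribed formulas fail at zero and have no lower limit, and neither document says what to do there.

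**Conclusion.** The point holds in limited form. That the term is undefined at 0 and unbounded below 1 mg/L is a property of the printed formulas and needs no assumption. The direction of the distortion for low positive values holds for any positive offset. Its size rests on the assumed +0.5 to +1 mg/L: 0.24 to 0.38 points for a fall from 20 to 0.5 mg/L, and 0.64 to 0.85 for a fall to 0.1 mg/L.

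The consequences are leverage and missing scores in Tables 9.1 and 9.2, and possible misclassification of DAS28-based severity where CRP is low. Neither can be quantified without the CRP distribution. The paired t-test on HAQ DI and all ESR-scored visits are unaffected. Priority is minor to moderate, and the point belongs with the reconciliation of the two DAS28 formulas.

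**What to change.** 1. In SAP 3.5.2, replace the single formula with separate ESR and CRP formulas identical to those in Protocol 9.2.4.7. This point takes no position on the unit of the global-assessment term.
2. In both documents, put an offset inside the CRP logarithm. The working proposal is ln(CRP + 1) with CRP in mg/L, to be confirmed against the scoring source that the protocol cites before it is adopted.
3. State one rule, in both documents, for a CRP of 0 or below the detection limit.
4. Derive DAS28 centrally wherever the components are recorded, and flag site-entered scores whose formula is unknown. The legible CRF items in Appendix C show no field for the patient's global assessment, so check first how far recomputation is possible.

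The cost is one changed term on top of the formula reconciliation, and a small re-derivation in the analysis program. DAS28-CRP changes become slightly smaller in patients who reach low CRP, and visits with CRP 0 gain a score.
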